1.1 Primary Objectives and Endpoint

1.1.1 Determine if 20% of ADT naïve men treated with concurrent EBRT and Radium-223 will not require ADT for progression by 15 months.
Endpoint: Determine the time from start of study therapy to start of ADT.

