7.4 Duration of Therapy

Subjects must be withdrawn from the study treatment for the following reasons:

Patients are expected to receive one neo-adjuvant dose of Radium-223 followed by EBRT for 2 to 6 weeks followed by 5 additional cycles of Radium-223. The treatment phase of the study should be completed in approximately 6 months pending dose delay or discontinuation

- Subject withdraws consent from the study treatment and/or study procedures. A subject must be removed from the trial at his/her own request or at the request of his/her legally acceptable representative. At any time during the trial and without giving reasons, a subject may decline to participate further. The subject will not suffer any disadvantage as a result.
- Subject is lost to follow-up.
- Death.
- Disease progression as defined in section 10

- In the event of disease progression, the subject will no longer receive study treatment, but will remain on the study for all follow-up evaluations, which include indicated imaging studies, lab draws, and all questionnaires.

Subjects may be withdrawn from the study for the following reasons:

- The subject is non-compliant with study drug, trial procedures, or both; including the use of anti-cancer therapy not prescribed by the study protocol.
- If, in the investigator's opinion, continuation of the trial would be harmful to the subject's well-being.
- The development of a second cancer.
- Development of an intercurrent illness or situation which would, in the judgment of the investigator, significantly affect assessments of clinical status and trial endpoints.
- Deterioration of ECOG performance status to 4.

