10.1 Primary Endpoint – 15 month Hormone Free Survival

The primary objective is to determine the hormone-therapy-free survival time for men treated with sequential EBRT and Radium-223 and determine whether it is a 20% risk reduction over the institutional comparator of 100% use of systemic therapy by 15 months. The primary outcome is 15 months hormone-free survival. Patients will remain on study treatment for the duration defined by the calendar or for disease progression. Patients will be followed up to determine the start of ADT which will be used to measure the primary end point.

For the purposes of this study, progression will be measured after the completion of EBRT and the delivery of Cycle 2 of Radium-223 and defined as either:

Biochemical Progression:

- For those subjects whose PSA is greater than 20ng/ml at baseline who do not have any PSA decrease after starting therapy: biochemical progression will be defined as a 10% rise over the baseline.

- For those subjects whose PSA is greater than 20ng/ml at baseline, who demonstrate decrease in PSA after study treatment: if the PSA nadir remains > 20ng/ml, biochemical progression will be defined as a PSA rise greater than 10% of the PSA nadir. If the PSA nadir is < 20ng/ml, biochemical progression will be defined as a PSA rise greater than 10% of the PSA nadir.

-For those subjects whose PSA is less than 20ng/ml at baseline: biochemical progression will be defined as PSA >20ng/ml and 10%.

*Any PSA test that would meet a failure definition has to be validated through Huntsman Cancer Institute or a Veterans Affairs Hospital with a repeat PSA test no sooner than 5 days and no later than 14 days from the initial notification of the result demonstrating progression.

OR

Radiographic progression: Any new, progressing, or reappearing lesion on Bone Scan, CT/Scan, or MRI compared to the same scan performed previously. Radiographic Progression will be determined by Prostate Cancer Clinical Trials Working Group (PCWG2) and RECIST 1.1 as described below (section 10.1.1).

* Of note: For a patient to meet radiographic progression criterion for appearance of new bone lesion only, the patient must demonstrate appearance of new bone disease, as confirmed by the treating radiation oncologist, and also meet the biochemical progression definition set out above.

OR

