11 STATISTICAL CONSIDERATIONS

The primary objective is to determine the hormone-therapy-free survival time for men treated with concurrent EBRT and Radium-223 and determine whether 20% of subjects do not meet the progression endpoint and require ADT at 15 months. The primary outcome is 15 months hormone- (or other systemic) therapy-free survival. The null hypothesis is that 99% of subjects will start systemic therapy within 15 months. The alternative hypothesis is that 80% of subjects will start systemic therapy within 15 months. With 20 evaluable subjects there will be 93% power for this alternative hypothesis using an exact binomial test at the one-sided 0.05 significance level. The null hypothesis will be rejected if 2 or more out of 20 subjects are not placed on systemic therapy within one year.

One of the secondary endpoints is to determine the hormone-therapy-free survival time for men treated with concurrent EBRT and Radium-223 and determine whether it is a 30% risk reduction over the SWOG intermittent ADT historic cohort. This secondary hypothesis will be tested only if the primary null hypothesis is rejected. The outcome for

this secondary hypothesis is 15 month hormone- (or other systemic) therapy-free survival. In 2012 a SWOG cooperative group trial reported that 78% of subjects on intermittent androgen therapy had resumed ADT within 15 months, and this proportion will be used as a null hypothesis. With 20 evaluable subjects, and a null hypothesis that 78% or more of patients will start systemic therapy within 15 months there will be 80% power to detect an alternative hypothesis that 48% or fewer will start systemic therapy within 15 month using an exact binomial test at one-sided alpha =0.05 significance level.

Additional, secondary endpoints are time to first skeletal related event (SRE), overall survival, PSA doubling time, overall survival and toxicities. All secondary endpoints will be evaluated descriptively. Time to first SRE, OS, and PSA doubling time will be analyzed via Kaplan-Meier product limit methods and associated 95% confidence intervals. Toxicities will be tabulated using CTAE version 4.0. The number and proportion of subjects with toxicities will be reported.

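### The primary rule does not classify evaluable men who leave before 15 months without ADT; read literally, it counts withdrawals and losses as successes, and two of them decide the trial

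*Combined protocol and SAP*

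**What the plan says.** Section 11 (Statistical Considerations) states both hypotheses as proportions starting therapy. For the null it writes: "The null hypothesis is that 99% of subjects will start systemic therapy within 15 months". Its alternative lowers that proportion to 80% over the same period. On sample size it says: "With 20 evaluable subjects there will be 93% power for this alternative hypothesis". The test is exact binomial, one-sided, at the 0.05 level. The null is "rejected if 2 or more out of 20 subjects are not placed on systemic therapy". That sentence then closes with a one-year window, although both hypotheses run to 15 months.

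The endpoint appears in three forms:

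- Section 1.1.1: "Determine the time from start of study therapy to start of ADT". Death is not mentioned.
- Section 10.1: "The primary outcome is 15 months hormone-free survival". The same paragraph says that follow-up for the start of ADT is what measures the endpoint.
- Section 11: a survival label again, widened to other systemic therapy, with no statement that death is an event.

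Three other places bear on the point. The opening of Section 10 calls a man evaluable once he has completed the first radium cycle, the EBRT and three or more radium cycles; it does not require follow-up to 15 months. Section 7.4 lists "Subject is lost to follow-up", with death and withdrawal of consent, as reasons for ending study treatment, and assigns these men no outcome for analysis. Section 11 names Kaplan-Meier methods only for skeletal events, overall survival and PSA doubling time.

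**The concern.** The primary test is a count, so each of the 20 men must be a success or a failure. The only criterion given is whether he was placed on systemic therapy. A man who becomes evaluable, withdraws at month 9 and has no ADT on record was not placed on therapy, so he counts towards rejection. Yet he says nothing about month 15.

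Take a hypothetical result: 18 men start ADT, one is known to be free of it at 15 months, and one was lost at month 9. Read literally, the count is 2 of 20 and the null is rejected. With the lost man as a failure it is 1 of 20, and with him excluded it is 1 of 19; neither rejects. The trial's conclusion then rests on a choice that the plan leaves open until the data are in hand. Section 11 also tests the comparison with the SWOG cohort only if the primary null is rejected, so a false rejection opens that test too.

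**Working it through.** **Inputs from Section 11.** n = 20; success probability 1 − 0.99 = 0.01 under the null and 1 − 0.80 = 0.20 under the alternative; reject at 2 or more successes.

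**Step 1. Reproduce the plan's figures.** P(X ≥ 2) = 1 − (1 − p)^20 − 20p(1 − p)^19.

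- p = 0.01: 1 − 0.8179 − 0.1652 = 0.0169, the attained type I error.
- p = 0.20: 1 − 0.0115 − 0.0576 = 0.9308, which agrees with the stated 93%.

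A cutoff of 1 would give a type I error of 0.182, so 2 is the smallest valid cutoff. The design arithmetic is sound.

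**Step 2. A fixed number of leavers counted as successes, null true.**

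- One leaver: one more success is needed among the other 19, so 1 − 0.99^19 = 1 − 0.8262 = 0.174.
- Two leavers: rejection is certain.

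**Step 3. A share d of men leaving without ADT.** The documents give no rate, so d is assumed. The null probability of being counted a success becomes 0.01 + 0.99d.

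| d (assumed) | Counted as success | Type I error |
|---|---|---|
| 0 | 1.00% | 1.7% |
| 1% | 1.99% | 5.9% |
| 2% | 2.98% | 11.9% |
| 5% | 5.95% | 33.6% |

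Solving for a type I error of 5% gives d of about 0.8%.

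**Step 4. From all-cause exit to exit without ADT.** Under the null nearly all men start therapy, so many who leave will already be correctly counted as failures. Assume constant, independent hazards over 15 months. The therapy hazard is a = −ln(0.01) = 4.605. For all-cause exit e, the exit hazard is b = −ln(1 − e). The share leaving untreated is q = b/(a + b) × [1 − exp(−(a + b))]. A further 0.01(1 − e) stay and are truly free of therapy.

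| e (assumed) | q | Truly free | Counted as success | Type I error |
|---|---|---|---|---|
| 2% | 0.43% | 0.98% | 1.41% | 3.2% |
| 5% | 1.09% | 0.95% | 2.04% | 6.2% |
| 10% | 2.22% | 0.90% | 3.12% | 12.8% |

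These depend on when men start ADT. If starts are instead spread evenly over the 15 months, the three type I errors are 6.0%, 15.4% and 34.2%. Both sets expose the full 15 months; requiring evaluability shortens the window and lowers them.

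**Step 5. Leavers counted as failures, cutoff kept.** Success probabilities become 0.01(1 − d) and 0.20(1 − d). At d = 5% the type I error is 1.5% and power 91.6%; at d = 10% they are 1.4% and 89.8%.

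**The case against.** The best defence is that the plan, read as a whole, already covers most of this.

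- **Death.** Section 11 itself labels the outcome as therapy-free survival shortly before it states the rule, and by common usage death is then a failure. This stands in part. A reader might infer that early deaths would plainly be scored as efficacy; the documents do not support that, because of this label. They do not settle the reverse either, since the hypotheses, the rule and Section 1.1.1 count therapy starts only. The label also says nothing about withdrawal or loss.
- **Who is counted.** A reader might infer that every man who leaves untreated becomes a success. That goes too far. The 20 are evaluable men, so those who leave before meeting the Section 10 definition are outside the count. But treatment lasts about 6 months, so most of the 15-month window comes after a man can become evaluable.
- **Follow-up.** Visits every 3 months for about two years, and continued follow-up after progression, should keep losses few. Eligibility requires a life expectancy of at least 2 years. This makes the problem less likely, but one or two men are enough.
- **Ordinary judgement.** A sensible analyst would probably not score a lost man as a success. Probably so, but excluding him, censoring him and failing him are all defensible, and the plan chooses none of them.

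**Conclusion.** The concern holds for evaluable men who withdraw or are lost before 15 months without recorded ADT: the rule as worded scores them as successes, and no other text overrides it. For deaths the plan is ambiguous rather than wrong. The cutoff and the stated power are correct.

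The firm figures are those that need no attrition rate: 17.4% type I error with one such man, certain rejection with two, and a tolerance of about 0.8%. A reader might infer from Step 3 that the trial's false-positive rate is a third, or even about two thirds (65.7% if 10% of men left untreated). The documents do not support that as an expectation. They give no attrition rate, and those figures need 5% to 10% of men to leave untreated under a null in which 99% start therapy. The same percentages taken as all-cause exit give about 6% to 13% with constant hazards, or 15% to 34% if therapy starts are evenly spread. The size is therefore uncertain, but the nominal 5% can be exceeded at ordinary rates of loss. Because this rule alone decides the primary result, it should be settled before analysis.

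**What to change.** In Section 11:

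1. Define a success as an evaluable man known to be alive at 15 months from first study treatment, with no ADT or other systemic antineoplastic therapy started.
2. In the exact binomial test, count deaths before 15 months and men of unknown status as failures, and name evaluable men as the denominator.
3. Give a Kaplan-Meier estimate at 15 months, with its confidence interval, as a sensitivity analysis.
4. Reconcile the one-year window in the rejection rule with the 15-month hypotheses.

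Use the same definition in Sections 1.1.1 and 10.1.

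The cost is one paragraph of wording, with no extra patients or procedures. Power falls as shown in Step 5, and the estimated success proportion is slightly less favourable because each lost man counts against the treatment. Scoring unknown status as failure is one convention among several. It suits this design because it keeps the type I error at or below the designed 1.7% whatever the rate of loss.

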In 2012 the SWOG cooperative group reported mature results of a randomized trial evaluating continuous versus intermittent androgen-deprivation therapy in men with hormone-naïve metastatic prostate cancer [14]. This trial was pivotal in cementing the care standard of immediate and continuous androgen deprivation in men with hormone-naïve metastatic prostate cancer, as a median survival benefit was noted over the intermittent cohort despite the fact that, statistically speaking, inferiority of intermittent therapy was not proven nor disproven. Men on the intermittent therapy arm did have significant improvement in quality of life domains. Notably, 78% of persons on the “intermittent” androgen therapy arm had to resume ADT within the first 15 months. Additionally, the investigators of this study classified patients as having “minimal” versus “extensive” disease as an analysis stratification. Minimal disease was defined as disease confined to the spine, pelvic bones, or lymph nodes. Those with visceral metastasis or other bony sites were classified as extensive. At 2 years, subjects with “minimal disease” receiving intermittent androgen deprivation had an 85% overall survival. We propose using the intermittent ADT cohort of the SWOG trial as a historic comparator of efficacy to this study.

Oligometastasis is a limited disease state that some have postulated may be curable. We will use best available ablative therapies to destroy gross tumor, and allow radium-223 to obliterate occult sites of metastasis that cannot be resolved by available imaging modalities. This may lead to delay of initiation of ADT or other antineoplastic systemic therapies, improved QOL, survival benefit, and potential cure.

Reference treatment is the standard of care use of immediate and continuous ADT as well as other reasonable standards of intermittent ADT, or other antineoplastic systemic therapies. Hypofractionated radiotherapy is not routinely used in asymptomatic lesions unless there is risk of impending pathologic injury.

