4 STUDY DESIGN

4.1 Description

This is a phase IIa, open-label, single-arm, and prospective study of hormone therapy-naïve men with oligometastatic prostate cancer to the bone. The study will test if treating the primary tumor sites and 5 or fewer sites of bone-only metastasis with external beam radiation with concomitant systemic Radium-223 will reduce the utilization of androgen deprivation therapy, improve QOL and improve OS over the comparator cohort of SWOG intermittent ADT historic cohort.

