5.2 Exclusion Criteria

Yes/No (Response of “yes” = patient ineligible)

5.2.1 Men with known brain or visceral metastases (except regional lymph nodes as defined by section 5.2.5) defined by CT or MRI Imaging of the abdomen or pelvis.

5.2.2 Men who have had LHRH agonist or antagonist hormone therapy in the prior six months.

5.2.3 Men with >5 validated bony metastases.

5.2.4 Men with baseline serum Testosterone <100 ng/dL.

5.2.5 Men with new or progressing lymphadenopathy clearly consistent with prostate metastasis on imaging or proven by pathologic biopsy at any time three months or later following their initial definitive therapy.

5.2.6 Prior or concurrent invasive malignancy (except non-melanomatous skin cancer) or lymphomatous/hematogenous malignancy unless continually disease free for a minimum of 3 years. All patients with in situ carcinoma are eligible for this study (for example, carcinoma in situ of the oral cavity is eligible) except patients with carcinoma of the bladder (including in situ bladder cancer or superficial bladder cancer).

5.2.7 Use of finasteride within 30 days prior to therapy PSA should not be obtained prior to 30 days after stopping finasteride.

5.2.8 Use of dutasteride within 90 days prior to therapy. PSA should not be obtained prior to 90 days after stopping dutasteride.

5.2.9 Previous or concurrent cytotoxic chemotherapy for prostate cancer.

5.2.10 Received systemic therapy with radionuclides (e.g., strontium-89, samarium-153, rhenium-186, or rhenium-188, or Radium Ra-223 dichloride) for the treatment of bony metastases.

5.2.11 Men who will receive radical prostatectomy to the primary site.

5.2.12 Imminent spinal cord compression based on clinical findings and/or magnetic resonance imaging (MRI). Spinal Cord compression will be defined as 360-degree circumferential obliteration of T2 cerebrospinal fluid signal around the spinal cord. Treatment should be completed for spinal cord compression.

5.2.13 Severe, active co-morbidity, defined as follows:

- Unstable angina and/or congestive heart failure requiring hospitalization within the last 6 months
- Transmural myocardial infarction within the last 6 months
- Acute bacterial or fungal infection requiring intravenous antibiotics at the time of registration
- Chronic obstructive pulmonary disease exacerbation or other respiratory illness requiring hospitalization or precluding study therapy at the time of registration

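### The secondary SWOG test borrows a 78% null from a different event and a wider population, so rejecting it cannot be read as a benefit over comparable men

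*Combined protocol and SAP*

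**What the plan says.** Objective 1.2.1 asks whether hormone-therapy-free survival shows a 30% risk reduction over the SWOG intermittent-ADT cohort, timed from the start of study therapy to the start of ADT. Section 11 turns this into a formal test, done only if the primary null is rejected. The benchmark is "In 2012 a SWOG cooperative group trial reported that 78% of subjects on intermittent androgen therapy had resumed ADT within 15 months", and the hypothesis is set up as "With 20 evaluable subjects, and a null hypothesis that 78% or more of patients will start systemic therapy within 15 months", with 80% power against 48% or fewer, "using an exact binomial test at one-sided alpha =0.05 significance level".

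Section 2 describes the source in the same terms: 78% of the intermittent "androgen therapy arm had to resume ADT within the first 15 months". It adds that the SWOG trial was stratified into minimal disease (spine, pelvic bones or lymph nodes) and extensive disease: "Those with visceral metastasis or other bony sites were classified as extensive". No resumption rate is given by stratum. A stratum figure appears only for two-year survival, where men with minimal disease "receiving intermittent androgen deprivation had an 85% overall survival".

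This trial takes men with no more than five bone metastases (Study Summary; 5.2.3) and excludes "Men with known brain or visceral metastases" (5.2.1, with an exception for regional nodes). Section 4.1 says the study will test whether treatment reduces ADT use and will "improve QOL and improve OS over the comparator cohort of SWOG intermittent ADT historic cohort".

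**The concern.** A single-arm test against a historical rate supports a claim of benefit only if that rate is what comparable men would show without the new treatment. The 78% differs from the trial's setting in two ways, and the plan addresses neither.

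- **Event.** Resuming ADT presupposes earlier ADT and an off-treatment interval. The trial counts the start of ADT or any other systemic therapy, from the start of study therapy. The plan does not say when the SWOG 15-month clock began.
- **Population.** The 78% is quoted for the intermittent arm with no restriction by stratum, in a trial that included extensive and visceral disease. This trial excludes visceral disease and more than five bone lesions. The plan uses the minimal-disease figure for survival but has none for the ADT rate.

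This is the only secondary objective with a formal test. As written, 9 of 20 men free of systemic therapy could be reported as a significant improvement over SWOG when case mix or the event definition might explain the result.

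**Working it through.** **Inputs (Section 11).** n = 20; null 78% start, so 22% free; alternative 48% start, so 52% free; exact binomial, one-sided 0.05.

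**Step 1: reproduce the plan's figure.** Let X be the number of men free of systemic therapy at 15 months, X ~ Binomial(20, p), with p = 1 − start rate. The critical value is the smallest r with P(X ≥ r | p = 0.22) ≤ 0.05.

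- P(X ≥ 8 | 0.22) = 0.0536, above 0.05, so r = 8 is not allowed.
- P(X ≥ 9 | 0.22) = 0.0186, so the rule is to reject at 9 or more free.
- Power: P(X ≥ 9 | 0.52) = 0.802, which matches the stated 80%.

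The 30% reduction is therefore absolute (78 − 30 = 48). A relative reduction (0.70 × 78% = 54.6% starting) would give power 0.600. The arithmetic is right, and the test holds its level against the null as written.

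**Step 2: set the benchmark beside the trial.**

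| | Source of the 78% | This trial |
|---|---|---|
| Event | Resuming ADT | Starting ADT or other systemic therapy |
| Prior ADT | Required by the word resume | Hormone-naïve, but 5.1.2 admits some men with earlier ADT |
| Disease | Intermittent arm, no stratum given; minimal and extensive strata in the trial | Five or fewer bone metastases, no visceral disease |
| Clock | Origin not stated | Start of study therapy |

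**Step 3: what the rule does if the comparable rate is not 78%.** The documents give no 15-month start rate for comparable men that could serve as a no-benefit benchmark for this test. The rates below other than 78% are therefore assumptions, taken on both sides of it. The rejection probability is P(X ≥ 9 | 20, 1 − start rate).

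| Assumed comparable start rate | Free without benefit | P(reject) |
|---|---|---|
| 99% | 1% | <0.0001 |
| 90% | 10% | 0.0001 |
| 80% | 20% | 0.010 |
| 78% (plan's null) | 22% | 0.019 |
| 75% | 25% | 0.041 |
| 70% | 30% | 0.113 |
| 65% | 35% | 0.238 |
| 60% | 40% | 0.404 |

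Solving P(X ≥ 9 | p) = 0.05 gives p = 0.2587, a start rate of 1 − 0.2587 = 74.1%. The error passes 0.05 only below about 74%, roughly four points under the null.

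**The case against.** The strongest reply is that nothing is wrong with the test as a test. Its null is 78% or more starting, and against that null the size is 0.0186. A reader might infer from the mismatch that the type I error is not the stated 0.05, or that it is inflated. The documents do not support that: the level holds for the hypothesis written, and for comparable men the error is unknown, not shown to be wrong. That part of the reply stands.

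The direction is also open. The only start rate the documents give for oligometastatic men is the institution's: 100% by 15 months in Section 2, and 99% in the Study Summary and the primary null. At 99% the rule would almost never reject. That rate reflects a practice of immediate ADT, so it does not settle the matter, but it prevents any claim that the error must run upward.

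Nor is the contrast between resuming and starting absolute. Criterion 5.1.2 admits men who had ADT with earlier radiotherapy if it ended more than six months before, and some with short bicalutamide use. For those men the trial event is itself a restart.

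Finally, the test is secondary and gated, and Section 2 lists SWOG among comparators that are not the primary aim. This limits the consequence but does not cure the defect: rejecting a 99% null says nothing about whether 78% is the right benchmark.

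**Conclusion.** The point holds in a limited form. The sample-size arithmetic and the nominal level are correct. What the plan lacks is a basis for treating 78% as the rate comparable men would show without benefit, so a rejection cannot be read as the improvement over SWOG that 1.2.1 seeks.

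The error for that comparison is unknown in size and direction. Over assumed comparable start rates from 99% down to 60% it runs from below 0.0001 to 0.404, and it stays within 0.05 if the rate is about 74% or higher. The range illustrates how the rule behaves; it does not estimate the true rate. The primary analysis is not affected.

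**What to change.** In Section 11 and objective 1.2.1, replace the formal test with an estimate: the proportion free of systemic therapy at 15 months with its exact 95% CI. Show it beside the SWOG figure, labelled as a descriptive comparison with a different event and population, and make no claim of a significant risk reduction over SWOG.

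Align 4.1 so that it does not promise a test of improvement over that cohort. Section 11 already says secondary endpoints are evaluated descriptively. That sentence follows a list of the other secondary endpoints and sits awkwardly with the formal test; this change makes it true of them all.

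Do not substitute the SWOG minimal-disease stratum as the null:

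- It is defined by site, not lesion count. A man with a single bone lesion outside the spine and pelvis is eligible here but would be extensive there.
- It includes nodal disease, whereas 5.2.5 excludes new or progressing nodal metastasis arising three months or more after definitive therapy.
- The event would still be resumption.
- The documents give no resumption rate for it.

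A lower null would also cost power at n = 20. With 48% starting as the alternative, a null of 70% needs 10 or more free (size 0.048, power 0.657), 65% needs 12 (0.020, 0.313), and 60% needs 13 (0.021, 0.174).

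The cost is a wording change and the loss of one gated secondary hypothesis test. The primary test and the sample size of 20 stay as they are.
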